5 STUDY DESIGN

5.1 Overall Design

This is an open-label, randomized, parallel group, single-dose study in healthy participants following IV administration of abatacept.

Participants will undergo screening evaluations to determine eligibility within 28 days prior to drug administration on Day 1. All participants are required to weigh between 60 and 100 kg, inclusive, and should be weighed using the same scale at each site.

Participants will be admitted to the clinical facility the day prior to dosing (Day -1) and will be confined until at least 24 hours post-dose.

[figure not shown]
On Day 1, eligible participants will be randomized in a 1:1 ratio. The randomization will be stratified by weight categories: ≥ 60 to < 70 kg, ≥ 70 to < 80 kg, ≥ 80 to < 90 kg, and ≥ 90 to ≤ 100 kg. Within each weight category, participants will be randomly assigned to abatacept drug product converted from drug substance by a new drug substance process (Treatment A) or abatacept drug product converted from drug substance by the current drug substance process (Treatment B) in a 1:1 ratio. A minimum of 10 participants per treatment per weight category are planned to be randomized.

In order to decrease variability, the goal of the treatment group assignment is to match each participant 1:1 by weight category to a participant with the opposite treatment assignment. Randomization numbers will be sequential within each weight category, starting with 1001, 2001, 3001, and 4001 for ≥ 60 to < 70 kg, ≥ 70 to < 80 kg, ≥ 80 to < 90 kg, and ≥ 90 to ≤ 100 kg weight categories, respectively.

On Day 1, participants will receive a single IV infusion of either Treatment A or Treatment B at a dose of 750 mg over approximately 30 minutes using a calibrated, constant-rate infusion pump.

The study design schematic is presented in [Figure 5.1-1](#).

Figure 5.1-1: Study Design Schematic

*Treatment A: IV infusion of single dose (750 mg) abatacept drug product converted from drug substance by a new process

**Treatment B: IV infusion of single dose (750 mg) abatacept drug product converted from drug substance by the current process

Abbreviations: IV = intravenous; PD = pharmacodynamic; PK = pharmacokinetic

Physical examinations, vital sign measurements, 12-lead electrocardiograms (ECG), and clinical laboratory evaluations will be performed at selected times throughout the dosing interval. Participants will be closely monitored for adverse events throughout the study. Blood samples for PK analysis, immunogenicity, [REDACTED] will be collected for up to 1680 hours (70 days) after study treatment administration. Approximately 260 mL of blood will be drawn from each participant during the study.

Participants will be closely monitored for AEs throughout the duration of the study. Participants will be discharged from the study following completion of evaluations on Day 71.

5.1.1 Data Monitoring Committee and Other External Committees

Not applicable.

5.2 Number of Participants

A sufficient number of participants will be screened to randomize approximately 140 participants into the study.

Approximately 70 participants will be assigned to each of the 2 treatment groups and will receive a single IV infusion of either Treatment A or Treatment B. Sample size determination is discussed in [Section 10.1](#).

6 STUDY POPULATION

For entry into the study, the following criteria **MUST** be met.

6.1 Inclusion Criteria

1) Signed Written Informed Consent

- a) Signed written informed consent must be obtained from the participants in accordance with requirements of the clinical facility's Institutional Review Board (IRB)/Independent Ethics Committee (IEC) prior to the initiation of any protocol-required procedures.

2) Type of Participant and Target Disease Characteristics

- a) Healthy participants as determined by no clinically significant deviation from normal in medical history, physical examination, vital signs, ECGs, and clinical laboratory determinations.
- b) Body weight will be between 60 and 100 kg, inclusive.

3) Age and Reproductive Status

- a) Males and Females, ages 18 or age of majority to 55 years, inclusive
- b) Women of childbearing potential (WOCBP) must have a negative serum pregnancy test within 24 hours prior to the start of study treatment.
- c) Women must not be breastfeeding
- d) WOCBP must agree to follow instructions for method(s) of contraception for the duration of treatment with abatacept plus 5 half-lives of abatacept (85 days) plus 30 days (duration of ovulatory cycle) for a total of 115 days post-treatment completion.
- e) Males who are sexually active with WOCBP must agree to follow instructions for method(s) of contraception ([Appendix 4](#)) for the duration of treatment with abatacept plus 5 half-lives of abatacept (85 days) plus the duration of spermatogenesis (90 days) for a total of 175 days after the last dose of study treatment. In addition, male participants must be willing to refrain from sperm donation during this time.
- f) Azoospermic males are exempt from contraceptive requirements. WOCBP who are continuously not heterosexually active are also exempt from contraceptive requirements, and still must undergo pregnancy testing as described in this section.

Investigators shall counsel WOCBP, and male participants who are sexually active with WOCBP, on the importance of pregnancy prevention and the implications of an unexpected pregnancy. Investigators shall advise on the use of highly effective methods of contraception, ([Appendix 4](#)) which have a failure rate of < 1% when used consistently and correctly.

6.2 Exclusion Criteria

1) Medical Conditions

- a) Participants who have a present malignancy or previous malignancy within the last 5 years prior to screening (except documented history of cured non-metastatic squamous or basal cell skin carcinoma or cervical carcinoma in situ). Participants who had a screening

procedure that is suspicious for malignancy, and in whom the possibility of malignancy cannot be reasonably excluded following additional clinical, laboratory or other diagnostic evaluations.

- b) Participants at risk for tuberculosis (TB) defined as follows:
 - i) Current clinical, radiographic, or laboratory evidence of active TB, even if currently being treated. Chest x-rays (posterior/anterior and lateral) obtained within the 6 months prior to screening and TB testing (IFN- α release assay or QuantiFERON_{TB} Gold) performed in the past month prior to screening will be accepted; however, a copy of the reports must be placed in the participant binder.
 - ii) A history of active TB unless there is documentation that the participant had received prior anti-TB treatment that was appropriate in duration and type according to local health authority guidelines.
- c) Participants with a history of herpes zoster
- d) Any acute or chronic bacterial infection in the previous 12 weeks of dosing
- e) Any recent infection requiring antibiotic treatment within 4 weeks of dosing
- f) Known or suspected infection, including infection with human immunodeficiency virus (HIV), hepatitis B or C viruses
- g) Presence of any factors that would predispose the participant to develop infection (eg, rectal fissures, poor dentition, open skin lesions)
- h) Known or suspected autoimmune disorder
- i) Any history of known or suspected congenital or acquired immunodeficiency state or condition that would compromise the participant's immune status
- j) Any significant acute or chronic medical illness
- k) Any major surgery within 4 weeks of study treatment administration
- l) Donation of blood to a blood bank or in a clinical study (except a screening visit or follow-up visit) within 4 weeks of study treatment administration (within 2 weeks of study treatment administration for plasma only)
- m) Blood transfusion within 4 weeks of study treatment administration
- n) Inability to be venipunctured and/or tolerate venous access
- o) Recent (within 6 months of study treatment administration) history of smoking or current smokers. This includes participants using electronic cigarettes or nicotine-containing products such as tobacco for chewing, nicotine patches, nicotine lozenges, or nicotine gum.
- p) Recent (within 6 months of study treatment administration) drug or alcohol abuse as defined in DSM IV, Diagnostic Criteria for Drug and Alcohol Abuse ([Appendix 5](#))
- q) Any other sound medical, psychiatric and/or social reason as determined by the investigator

2) Prior/Concomitant Therapy

- a) Inability to comply with restrictions and prohibited treatments as listed in [Section 7.7](#).

3) Physical and Laboratory Test Findings

- a) Evidence of organ dysfunction or any clinically significant deviation from normal in physical examination, vital signs, ECG, or clinical laboratory determinations beyond what

is consistent with the target population. Estimated glomerular filtration rate (based on the MDRD equation) $< 70 \text{ mL/min/1.73 m}^2$

- b) Any of the following on 12-lead ECG prior to study treatment administration, confirmed by repeat
 - i) $\text{PR} \geq 210 \text{ msec}$
 - ii) $\text{QRS} \geq 120 \text{ msec}$
 - iii) $\text{QT} \geq 500 \text{ msec}$
 - iv) $\text{QTcF} \geq 450 \text{ msec}$ for males, $\geq 470 \text{ msec}$ for females
- c) Any of the following clinical laboratory evaluation, at screening or Day -1, confirmed by repeat:
 - i) Alanine aminotransferase (ALT) $> \text{ULN}$
 - ii) Aspartate aminotransferase (AST) $> \text{ULN}$
 - iii) Direct bilirubin $> \text{ULN}$
 - iv) Total bilirubin $> \text{ULN}$
 - v) LDH $> \text{ULN}$
 - vi) Serum creatinine $> \text{ULN}$
 - vii) Creatine kinase (CK) $> 4 \times \text{ULN}$
 - viii) Electrolytes (sodium, potassium, chloride, calcium, or phosphorus) outside of the reference range deemed to be clinically significant by the investigator
 - ix) Complete blood count (including platelets) outside the reference range deemed to be clinically significant by the investigator
- d) Positive urine screen for drugs of abuse including cotinine
- e) Positive alcohol urine or breath test
- f) Positive blood screen for hepatitis C antibody, hepatitis B surface antigen (HBsAg), hepatitis B core antigen antibody (anti-HBc), or HIV-1 and -2 antibody
- g) Clinically significant abnormal thyroid-stimulating hormone (TSH) at screening. A reflex test for free triiodothyronine (T3)/free thyroxine (T4) will be completed for TSH values out of the reference range to assist in the determination of clinical significance.

4) Allergies and Adverse Drug Reaction

- a) History of allergy to abatacept or related compounds
- b) History of any significant drug allergy (such as anaphylaxis or hepatotoxicity)

5) Other Exclusion Criteria

- a) Prisoners or participants who are involuntarily incarcerated. (Note: under specific circumstances a person who has been imprisoned may be included as a participant. Strict conditions apply and Bristol-Myers Squibb approval is required.)
- b) Participants who are compulsorily detained for treatment of either a psychiatric or physical (eg, infectious disease) illness
- c) Inability to comply with restrictions as listed in [Section 6.3 Lifestyle Restrictions](#)

Eligibility criteria for this study have been carefully considered to ensure the safety of the study participants and that the results of the study can be used. It is imperative that participants fully meet all eligibility criteria.

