Tuberculosis (TB) Screening	X		QuantiFERON [®] TB Gold test. A QuantiFERON-TB Gold test performed within 4 weeks of dosing on Day 1 is acceptable as long as there is documentation of a negative result.
Hematology and Serum Chemistry	X	X	Screening results must be available and reviewed prior to admission on Day -1. Day -1 results must be available and reviewed prior to dosing on Day 1. See Section 9.4.4 .
Thyroid Function Test	X		Thyroid-stimulating hormone (TSH) with reflex to free thyroxine (free T4), free triiodothyronine (free T3). Results must be available and reviewed prior to admission on Day -1.
Urinalysis	X	X	Screening results must be available and reviewed prior to admission on Day -1. Day -1 results must be available and reviewed prior to dosing on Day 1. See Section 9.4.4
Chest X-ray	X		A posterior-anterior and lateral chest x-ray will be performed. Results must be available and reviewed prior to admission on Day -1. See Section 9.4.7
Adverse Event Reporting			
Monitor for Serious Adverse Events	X	X	All SAEs must be collected from the date of participant’s written consent until 101 days post dose. If a participant prematurely discontinues, all SAEs must be collected 30 days post last visit.

Table 2-2: On Treatment Procedural Outline(IM101682)

Procedure	Day 1	Day 2	Day 4	Day 8	Day 15	Day 22	Day 29 ± 2 Days	Day 43 ± 2 Days	Day 57 ± 2 Days	Day 71 ± 2 Days Study Discharge ^a	Notes
Safety Assessments											
Physical Examination (PE)		X					X			X	
Targeted PE	X										Day 1 predose. Targeted examination of skin. Photographs may be taken of any areas affected by rash that develop after the start of the infusion (including evolving changes). See Section 9.4.1.1 . Continued monitoring of rashes will occur as needed. Targeted examination of other systems based on clinical symptoms.
Inspection of IV injection site	X										Predose and 1 hour post end of the infusion. Additional inspections (including photography of any changes) may be conducted as warranted. See Section 9.4.1.1.
Physical Measurements										X	Weight only.
Vital Signs	X ^b	X	X	X	X	X	X	X	X	X	See note in screening procedures.
Electrocardiogram (ECGs)	X ^c									X	See note in screening procedures.
	■	■	■	■	■	■	■	■	■	■	

Table 2-2: On Treatment Procedural Outline(IM101682)

Procedure	Day 1	Day 2	Day 4	Day 8	Day 15	Day 22	Day 29 ± 2 Days	Day 43 ± 2 Days	Day 57 ± 2 Days	Day 71 ± 2 Days Study Discharge ^a	Notes
Laboratory Tests											

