For the predose assessments on Day 1 PK, immunogenicity, and PD samples, ECG, vital signs, and examinations may be obtained up to 60 minutes prior to study treatment administration.

[REDACTED]

[REDACTED]

[REDACTED]

This study is in healthy participants, a population that would not receive any health benefit from participating in this study. Although this single dose study for normal healthy participants should not pose an unacceptable health risk to participants based on the established safety profile of abatacept, in order to minimize the overall risk to participants, this protocol has inclusion and exclusion criteria appropriate to the population and proposed dosing, exclusionary screening tests (tuberculosis testing, chest x-ray, medical history, physical examination), and specific follow-up safety assessments. Adverse events and SAEs will be reviewed on an ongoing basis by the BMS Medical Monitor and by the BMS Pharmacovigilance Department to look for trends and any safety issues.

Risks from the PK, immunogenicity, and clinical safety phlebotomy procedures are standard and include infection, bleeding, bruising, blood clot formation, discomfort at the injection site, and (rarely) fainting.

More detailed information about the known and expected benefits and risks and reasonably anticipated AEs of abatacept may be found in the Investigator’s Brochure⁴, an addendum to the Investigator’s Brochure³³, and the prescribing information.¹

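### Two TB screening rules conflict: criterion 1(b)(i) accepts a release assay up to about 56 to 59 days old with no stated result, while Table 2-1 asks for a negative QuantiFERON within 4 weeks of dosing

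*Protocol*

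**What the plan says.** All references are to the protocol unless stated.

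- **Section 6.2, criterion 1(b)(i)** excludes "Current clinical, radiographic, or laboratory evidence of active TB, even if currently being treated". The same item accepts a QuantiFERON or another interferon release assay "performed in the past month prior to screening will be accepted; however, a copy of the reports must be placed in the participant binder". It names no result.
- **Section 6.2, criterion 1(b)(ii)** excludes "A history of active TB unless there is documentation that the participant had received prior anti-TB treatment" of suitable type and duration.
- **Section 6.2, criteria 3(d) to 3(f)** name other screening results that exclude: drugs of abuse and cotinine, alcohol, hepatitis B and C, and HIV. No TB assay is among them.
- **Table 2-1, TB screening row,** schedules a QuantiFERON at the Screening Visit. Its note says that a "test performed within 4 weeks of dosing on Day 1 is acceptable as long as there is documentation of a negative result".
- **The benefit/risk text** (Section 3.3 by the table of contents) counts TB testing among the "exclusionary screening tests (tuberculosis testing, chest x-ray, medical history, physical examination" and so on, used to limit risk to volunteers who cannot benefit.
- **Section 9.4.4** lists the QuantiFERON at screening without a required result. **Section 9.4.7** does make a TB-negative chest x-ray a condition of entry.
- **Section 9** makes the Schedule of Activities binding, allows no waivers, and lets routine tests done before consent count only if they fall within the Schedule's timeframe.
- **Section 5.1** sets screening within 28 days before dosing. The SAP repeats this in its Section 2.1 and has no TB rule.

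**The concern.** A site deciding eligibility checks the list in Section 6.2. On TB, that list and the Schedule of Activities say different things about the same blood test. One accepts an older result and asks only that it be filed. The other sets a shorter limit and asks for a negative result. The list also does not contain the criterion that the benefit/risk text leads one to expect, namely that a positive TB assay excludes.

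At stake is a safety screen for healthy people who get no benefit from the single dose, and whether sites apply it in the same way. The pharmacokinetic comparison is not at stake: Cmax, AUC(INF), the sample size and the power do not depend on this rule.

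**Working it through.** The plan gives no figure to reproduce. The check is a comparison of the rules and some date arithmetic.

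**1. Oldest test each rule accepts.** Inputs:
- s = days from screening to dosing, at most 28 (Section 5.1)
- m = one month before screening (criterion 1(b)(i)); the protocol does not define a month, so I assume 28 to 31 days
- Table 2-1 limit = 4 weeks × 7 = 28 days before dosing

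Oldest test under 1(b)(i) = s + m. Gap to Table 2-1 = s + m − 28.

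| Screening before dosing (s) | Oldest test under 1(b)(i) | Gap to Table 2-1 |
|---|---|---|
| 7 days | 7 + 28 = 35 to 7 + 31 = 38 days | 7 to 10 days |
| 14 days | 14 + 28 = 42 to 14 + 31 = 45 days | 14 to 17 days |
| 28 days (maximum) | 28 + 28 = 56 to 28 + 31 = 59 days | 28 to 31 days |

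The maximum is 56 / 7 = 8.0 to 59 / 7 = 8.4 weeks, about twice the Table 2-1 limit. The rows for 7 and 14 days are illustrations. They show that the windows disagree whenever screening precedes dosing, not only at the extreme.

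**2. Required result and assay.**

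| | Criterion 1(b)(i) | Table 2-1 note |
|---|---|---|
| Assay | QuantiFERON or another release assay | QuantiFERON only |
| Window | one month before screening | 4 weeks before dosing |
| Result | none stated; report filed | documented negative |
| Form | part of an exclusion criterion | condition on which test is acceptable |

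**3. One case through both rules.** A volunteer is screened 20 days before dosing and brings an assay done 20 days before that. At dosing the test is 20 + 20 = 40 days old. Criterion 1(b)(i) accepts it. Table 2-1 does not, because 40 exceeds 28. If it was a routine-care test, Section 9 sides with Table 2-1.

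**4. What excludes a positive volunteer with no symptoms and a clear chest x-ray?** In the readable text:
- the Table 2-1 note, through Section 9;
- 1(b)(i), if laboratory evidence is taken to include the assay, although that item is limited to active TB;
- judgment under general criteria: 1(d) on bacterial infection in the 12 weeks before dosing, 1(f) ("Known or suspected infection, including infection with human immunodeficiency virus (HIV), hepatitis B or C viruses"), 1(q) ("Any other sound medical, psychiatric and/or social reason as determined by the investigator"), 3(a) and inclusion 2(a) on clinically significant laboratory deviations.

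None of the criteria in Sections 6.1 and 6.2 names a positive release assay.

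**The case against.** The strongest reply is that the protocol, followed in full, already gives the right answer. Table 2-1 puts a QuantiFERON at the Screening Visit, and screening lies within 28 days of dosing, so that test falls under the note and needs a documented negative result. Section 9 makes the Schedule binding and holds routine tests done before consent to its timeframe. Criterion 1(b)(i) says that an older test is accepted, not that it replaces the scheduled one. Criterion 1(b) is also about people at risk for TB, and its reference to laboratory evidence is followed directly by a sentence on x-ray and TB tests, so reading it to include the assay is natural. Placing a required result outside 6.2 is also this protocol's habit, as the x-ray rule in Section 9.4.7 shows.

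Most of this stands. A reader might infer from 1(b)(i) that a positive volunteer could be dosed, or that older tests and other assays escape any need for a negative result. The documents support neither inference: a strict reading through Section 9 arrives at a negative QuantiFERON within 4 weeks, and the general criteria give further grounds to exclude. Section 7.7 is also redacted. Exclusion 2(a) refers to it, and the summary of changes shows a subsection there on infectious complications, which may deal with TB.

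The reply does not remove the conflict. To reach the 4-week limit, a site must let Section 9 override an acceptance stated in the exclusion criteria. The broad reading of laboratory evidence still meets the restriction to active TB, and the general criteria depend on the investigator's view.

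**Conclusion.** Wrong as written, and minor. Criterion 1(b)(i) and the Table 2-1 note conflict on the age of an acceptable TB test, on the assay, and on whether a negative result is required. The age limits differ by at most 28 to 31 days (56 to 59 days against 28), assuming a month of 28 to 31 days and screening on the earliest permitted day. The benefit/risk text calls TB testing exclusionary, but no criterion in 6.2 names the result that excludes.

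The conclusion covers the readable text only. It does not say that a positive volunteer would be dosed. The number affected cannot be estimated, because the documents give neither a rate of positive assays nor the share of volunteers who would bring an older result. The biocomparability conclusion is unaffected.

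**What to change.** Make two edits to Section 6.2:

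1. Add a line in 1(b), or beside 3(f), that excludes any participant without a documented negative QuantiFERON-TB Gold, or other accepted release assay, within 4 weeks before dosing. State that a positive result excludes, as does an indeterminate result not resolved on repeat. The indeterminate case is my proposal, since the readable text does not address it. Section 6.4.1 already permits retesting.
2. Change the test window in 1(b)(i) to 4 weeks before dosing, to match Table 2-1. If another release assay is to remain acceptable, name it in the Table 2-1 note too.

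The sponsor should also say which rule prevails for someone with adequately treated past TB, whom 1(b)(ii) does not exclude but the new line would if the assay is positive.

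No new test is needed, because Table 2-1 already schedules a QuantiFERON at screening. The cost is possibly a few more screen failures, and older outside results could no longer be used.

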6.3 Lifestyle Restrictions

6.3.1 Meals and Dietary Restrictions

- Participants are required to fast (nothing to eat or drink except water) for 1 hour prior to study treatment administration. Participants are required to continue to fast (nothing to eat or drink except water) for at least 1 hour after study treatment administration. Water may be consumed ad libitum at other times.
- Participants are required to fast (nothing to eat or drink except water) for 10 hours before blood laboratory evaluations.
- On Day 1:
 - A light breakfast (see [Appendix 6](#)) will be served approximately 1 hour post the end of the study treatment administration.
 - A standard lunch will be served approximately 4 hours post the end of study treatment administration.
 - A standard dinner will be served approximately 8 hours after post the end of study treatment administration.
 - A standard light snack will be served approximately 12 hours after post the end of study treatment administration.

